3.2. STUDY GROUPS

Eligible participants will be randomised in equal proportion into 4 groups: vitamin D supplement, dietary intervention, sun exposure and wait list control.

3.3. NUMBER OF PARTICIPANTS*

By setting the significance level α =0.05, the power 1- β = 0.8. Based on Campbell & Machin (1993) formula: m=($Z\alpha$ + $Z2\beta$)2{ π 1(1- π 1)+ π 2(1- π 2)}/ δ 2, ($Z\alpha$ + $Z2\beta$)2 = 7.849, δ = π 2- π 1=0.7-0.35= 0.35; m=28. Therefore the sample size for each group in the current study is calculated to be at least 28, total recruit participants required to be at least 112. With the consideration of a dropout rate 10%-20%, it is planned to recruit 123-134 participants in total with 31-34 participants in each group.

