THE ROLE OF VITAMIN D IN CONTROLLING AND REDUCING DM RISKS (D4D)

Version IV November 2018

SYNOPSIS

Protocol title: The Role of Vitamin D in Controlling and Reducing DM Risks (D4D)

Protocol version: Version IV

LIST OF INVESTIGATORS

Principal Investigator: [name]

Signature: Date:

Organisation: School of Life Sciences, University of Technology, Sydney Address: School of Life Sciences, University of Technology, Sydney

[contact]

Email: [contact]

Co Investigator: Associate [name]

Signature: Date:

Organisation: School of Life Sciences, Program Director, School of Medical and Molecular

Biosciences, University of Technology, Sydney

Address: School of Life Sciences, Program Director, School of Medical and Molecular Biosciences,

University of Technology, Sydney [contact]

Email: [contact]

Co Investigator: Adjunct [name]

Signature: Date:

Organisation: School of Life Sciences, University of Technology, Sydney Address: Specialist Medical Services, [name]

Email: [contact]

Summary

Study title The Role of Vitamin D in Controlling and Reducing DM Risks (D4D)

Protocol version

Version IV

Objectives

To determine if vitamin D can benefit DM and the impacts from different heterogeneous vitamin D sources.

Study design

The D4D trial is designed as a multi-centre, single-blind, randomized, parallel group, superiority study to determine the role of Vitamin D from the oral supplement, sun exposure and dietary invention in controlling and reducing DM risks.

Planned sample size

120-140 participants

Selection criteria

1) Aged ≥ 18 years old; 2) Diagnosed with DM in the preceding 12 months, and not on diabetic medication or insulin treatment; 3) Serum 25OHD is between 28 nmol/l and 85 nmol/l and not on vitamin D supplements or any relevant medications; 4) Do not have thyroid diseases, liver impairment, renal failure, cancer, osteoporosis, dementia, mental diseases or taking relevant medications; 5) Not pregnant or breastfeeding women.

Study procedures

Eligible participants will be randomized in equal proportion into one of 4 groups: vitamin D supplement, dietary intervention, sun exposure and wait list control.

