The vitamin D supplement group will be given an oral vitamin D supplement to ingest, dosage set as 500 IU per day. The dietary intervention group will be asked to follow a 'vitamin D food resources' list to obtain 10-15 μ g/d of vitamin D from food. The sun exposure group will be required to expose about 15% of body surface (hands, face and arms) to natural sunlight anytime from 10am to 4pm for 3-4 minutes/d from December to January, or 8 minutes/d from July to August or 10— 11 min/d from February to June or September to November, to get approximately 12.5 μ g/d of vitamin D per day. No interventions will be given to the wait list control group.

The total study period of the trial is 9 months. A face-to-face adherence reminder and examination session will occur at baseline and on a monthly basis. A blood test of vitamin D level and DM biomarkers will be obtained at baseline, and at the 3rd month and 9th month session. Participants who report with any side effects or upset symptoms will be assessed by study therapists and excluded from the trial once being confirmed.

Statistical considerations

Sample size calculation: By setting the significance level α =0.05, the power 1- β = 0.8 based on Campbell & Machin (1993) formula: m=(Z α + Z2 β)2{ π 1(1- π 1)+ π 2(1- π 2)}/ δ 2, (Z α + Z2 β)2 = 7.849, δ = π 2- π 1=0.7-0.35= 0.35; m=28. Therefore for the current study, the sample size of each group is calculated as at least 28, hence it requires at least 112 participants in total. With the consideration of a dropout rate 10%-20%, it is planned to recruit 31-34 participants per group with 123-134 participants in total.

Analysis plan: Data are expressed as means ± SDs. Initially, the Kolmogorov–Smirnov goodness-of-fit test will be used to assess the normal distribution of variables. Secondly, two-factor repeated-measures analysis of variance (ANOVA) will be used with Bonferroni correction in the current trial with time stages and

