8. STATISTICAL CONSIDERATIONS*

By setting the significance level α =0.05, the power 1- β = 0.8 based on Campbell & Machin (1993) formula: m=(Z α + Z2 β)2{ π 1(1- π 1)+ π 2(1- π 2)}/ δ 2, (Z α + Z2 β)2 = 7.849, δ = π 2- π 1=0.7-0.35= 0.35; therefore m=28. Therefore the sample size for each group in the current study was calculated to be

at least 28, with at least 112 in total. With the consideration of a dropout rate 10%-20%, it is planned to recruit 123-134 participants in total hence 31-34 participants for each group.

Data are expressed as means ± SDs. Initially, the Kolmogorov–Smirnov goodness-of-fit test will be used to assess the normal distribution of the values. Secondly, two-factor repeated-measures analysis of variance (ANOVA) with a Bonferroni correction will be used in the current trial with time stages and interventions as factors. Tukey's post-hoc comparison will be applied to identify the differences between four intervention groups at 3 months and 9 months in the case of significant interaction finding in ANOVA. Thirdly, correlations between variables will be evaluated by using either a Pearson (r) (for data with normal distribution) or a Spearman (rs) (for data with no normal distribution) correlation. A p-value <0.05 is considered to be statistically significant. All statistical analyses will be computed using the Statistical Package for Social Science version 17 (SPSS, Chicago, IL, USA). Missing values are to be treated according to the last observation carried forward (LOCF) method and will be assessed via sensitivity analysis.

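### The dropout allowance multiplies 112 by 1.1 to 1.2 instead of dividing by 0.9 to 0.8, so the upper target is 134 where 20% dropout needs 140, and the Synopsis gives a different range (minor numerical correction)

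*Protocol*

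**What the plan says.** Section 3.3 sets the design values ("By setting the significance level α =0.05, the power 1- β = 0.8") and the response rates ("π 2- π 1=0.7-0.35= 0.35; m=28"). From these it derives a minimum, which it puts at 112 for the whole trial: "the sample size for each group in the current study is calculated to be at least 28, total recruit participants required to be at least" that number. Section 3.2 fixes equal allocation: "Eligible participants will be randomised in equal proportion into 4 groups".

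The dropout allowance follows in section 3.3: "With the consideration of a dropout rate 10%-20%, it is planned to recruit 123-134 participants in total with 31-34 participants in each group". The same figures appear in section 8 ("it is planned to recruit 123-134 participants in total hence 31-34 participants for each group") and in the Synopsis under Statistical considerations ("it is planned to recruit 31-34 participants per group with 123-134 participants in total").

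The Synopsis entry for planned sample size gives something else: "120-140 participants". The protocol does not say how the allowance was calculated or why the two ranges differ.

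**The concern.** An allowance for dropout should leave the required number after the losses. If a fraction d of those recruited is lost, then N(1 − d) must be at least 112, so N = 112/(1 − d). The stated totals look like 112(1 + d), which always falls short, and by more as d grows. At stake is whether the minimum of 28 per group survives the dropout that the protocol itself anticipates.

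There is also a practical issue. Recruitment stopped at 120 would satisfy the planned size in the Synopsis but fall below the range in sections 3.3 and 8.

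**Working it through.** **Inputs (section 3.3, with four equal groups from section 3.2).** Response rates 0.35 and 0.70; multiplier 7.849, which is (1.960 + 0.842)² and so implies two-sided α = 0.05 with 80% power; dropout 10% to 20%.

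**1. Base size.** m = 7.849 × (0.35 × 0.65 + 0.70 × 0.30)/0.35² = 7.849 × 0.4375/0.1225 = 28.03, stated as 28. Four groups give 112. The base reproduces, with nothing to spare. It is taken as given here.

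**2. Reproducing the stated recruitment figures.**
- 112 × 1.1 = 123.2 and 112 × 1.2 = 134.4, which are the stated 123 and 134.
- 28 × 1.1 = 30.8 and 28 × 1.2 = 33.6, which round to the stated 31 and 34.

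The protocol does not name its method, but multiplying by (1 + d) reproduces all four numbers. Dividing by (1 − d) does not.

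**3. What the allowance should give.**
- 10% dropout: 112/0.9 = 124.4, so 125; per group 28/0.9 = 31.1, so 32 (128 with equal groups).
- 20% dropout: 112/0.8 = 140; per group 28/0.8 = 35.

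**4. Completers and power.** Power is Φ(0.35/√(0.4375/n) − 1.960), the protocol's unpooled formula turned round, with n the completers per group. At n = 28 it gives 80.0%.

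| Recruited | Dropout | Completers | Per group | Power |
|---|---|---|---|---|
| 123 | 10% | 110.7 | 27.7 | 79.5% |
| 134 | 20% | 107.2 | 26.8 | 78.2% |
| 136 (34 × 4) | 20% | 108.8 | 27.2 | 78.8% |
| 140 (35 × 4) | 20% | 112.0 | 28.0 | 80.0% |
| 120 (Synopsis) | 10% | 108.0 | 27.0 | 78.5% |
| 120 (Synopsis), worst case | 20% | 96.0 | 24.0 | 73.6% |

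The per-group figures show the same pattern: 31 × 0.9 = 27.9 and 34 × 0.8 = 27.2, both under 28.

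**5. Dropout each target tolerates before falling below 112.** For 134: 1 − 112/134 = 16.4%. For 136: 1 − 112/136 = 17.6%. For 140: 20%.

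**6. The totals side by side.** 31 × 4 = 124 and 34 × 4 = 136, against 123-134. This difference is rounding, since neither 123 nor 134 divides by four. The 120-140 in the Synopsis is not a rounding of either pair.

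**The case against.** The best defence is that the error is too small to matter. At matched dropout the loss is 0.5 points of power at 10% and under 2 points at 20%. At the lower end, 123 against 125 is within the precision of a base rounded from 28.03. A recruitment of 134 still leaves 120.6 completers at 10% dropout, and 134 to 136 recruits hold 112 over most of the planned dropout range. All of this stands, and it is why the point is minor.

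A reader might infer that power falls to about 74%. The protocol does not support that as the expected result. The figure pairs the lowest Synopsis total with the highest dropout rate; at 10% dropout the same 120 gives about 78.5%. A reader might also count three conflicting ranges. Only the 120-140 in the Synopsis differs in substance, and even that range contains 123-134, and its upper end is the correct figure for 20% dropout.

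Two further objections carry less weight. Section 8 treats missing values by last observation carried forward, so some dropouts may still enter the analysis, and the counts above are therefore completers. But the protocol itself enlarges the sample for dropout to protect 112, so that enlargement should do what it sets out to do. It is also fair that these power figures belong to a two-proportion comparison, whereas section 2.1 names HbA1c as the measure and section 8 plans a repeated-measures analysis of variance. They measure the error on the protocol's own scale and are not a forecast of the trial's power for HbA1c.

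**Conclusion.** The allowance is calculated wrongly as written. For 10% to 20% dropout the range should be 125-140 in total (32-35 per group in whole participants), where the protocol has 123-134 (31-34 per group). The difference that counts is 134 against 140 at 20% dropout: about 107 completers in place of 112, and about 78% power in place of 80% by the protocol's formula. Separately, the planned size in the Synopsis and the target in the body are not the same.

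It would go too far to say that the minimum is missed throughout the planned dropout range, or that the trial is materially underpowered because of this. The shortfall holds for each figure at the dropout rate it was built for. The conclusion assumes that 28 per group is the right base, that dropout means a fraction of those recruited, and that losses are equal across the four groups. Severity: minor, a numerical correction.

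**What to change.** State one recruitment target, in the same words, in all four places: the Synopsis entry for planned sample size, the Synopsis statistical considerations, section 3.3 and section 8. Either option removes both 120-140 and 123-134:

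- **35 per group, 140 in total.** This keeps 28 per group at 20% dropout. It is four more than 34 × 4 = 136 and is already the top of the Synopsis range.
- **34 per group, 136 in total.** This is already the upper per-group figure. Add that it retains 28 per group only up to about 17.6% dropout, and that at 20% power is about 79% by the protocol's formula.

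Whichever is chosen, show the calculation as n/(1 − d). The cost is a text correction in four places. The second option needs no recruitment beyond the 34 per group already stated.

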3.4. NUMBER OF CENTRES

Participants are to be recruited primarily from the Earlwood Medical Centre (EMC), which is a community medical centre located in south central Sydney. Participants are also to be recruited from the Bangor Medical Centre located in south Sydney. All the following research visits including assessment and data collection will only be conducted in the Earlwood Medical Centre.

3.5. DURATION

The D4D research is planned to commence in late-2018 and expected to complete by 2021. The participants will be involved during the intervention phase for 9 months. The expected duration of the recruitment phase is 10-12 months.

4. PARTICIPANT SECTION

4.1. INCLUSION CRITERIA*

Participants eligible for the trial should comply with all of the following criteria:

1) Aged ≥ 18 years old; 2) Diagnosed with DM in the preceding 12 months, and not on diabetic medication or insulin treatment; 3) Serum 25OHD is between 28 nmol/l and 85 nmol/l and not on vitamin D supplements or any relevant medications; 4) Do not have thyroid diseases, liver impairment, renal failure, cancer, osteoporosis, dementia, mental diseases or taking relevant medications; 5) Not pregnant or breastfeeding women.

4.2. EXCLUSION CRITERIA*

Participants are not eligible for the trial if they are:

1) Unable to give written informed consent or follow the instructions in current trial; 2) are already on vitamin D supplementation or relevant medications; 3) have liver impairment, renal failure (eGFR <50 ml/min), cancer, osteoporosis, dementia, mental disease, and thyroid diseases including hyperparathyroidism, hypercalcaemia, or taking any relevant medications; 4) are < 18 years old or are pregnant or breastfeeding women. 5) are vegen and can not ingest any animal product.

5. STUDY OUTLINE*

5.1. STUDY FLOW CHART

Participants screening & recruitment

Complete consent

Randomisation

A. Vitamin D
Supplement
Take the vitamin D
supplement 500 IU/d

B. Dietary intake
Follow the
prescribed dietary
plan to obtain 10-15
µg/d of vitamin D

C. Sun exposure

Expose about 15% of body surface (hands, face and arms) under the sun anytime from 10am to 4pm for 3-4 min/d from December to January, or 8 min/d from July to August or 10–11 min/d from February to June or September to November. This will provide approximately 12.5 µg/d of vitamin D

D. Wait list Control Nil intervention

Baseline assessment

- Information delivery session
- Problem and strategy session
- Anthropometry assessment for all: weight, height, BMI, waist & hip ratio
- Blood test (HbA1c, BSL, insulin and serum 25 OHD)

Monthly follow up session

- Anthropometry assessment for all: weight, BMI, waist & hip ratio
- Supplement group: pill count
- Diet group: collect data from smartphont application or paperbased diary
- Sun exposure group: collect data from sun exposure questionnaire
- Adherence assessment
- Problem and strategy assessment

3rd month assessment

- Anthropometry assessment for all: weight, BMI, waist & hip ratio
- Supplement group: pill count
- Diet group: collect data from smartphont application or paperbased diary
- Sun exposure group: collect data from sun exposure questionnaire
- Adherence assessment
- Problem and strategy assessment
- Blood test (HbA1c, BSL, insulin and serum 25 OHD)

Monthly follow up session: As above

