5.2. INVESTIGATION PLAN*

List Interventions	Baseline assessment	3 rd month visit	9 th month visit	Other monthly visits
Training plans	Prior to baseline assessment	N/A	N/A	N/A
Information delivery session & Informed Consent	V	N/A	N/A	N/A
Inclusion / Exclusion criteria	Prior to the initial visit	N/A	N/A	N/A
Anthropometry assessment	✓	√	✓	√
Dietary intake exam	✓	✓	✓	✓
Sun exposure exam	✓	✓	✓	✓
Pill count	N/A	✓	✓	✓
Adherence assessment with Problem & strategies session	√	√	√	√
Adverse Event Assessment	✓	✓	✓	√
Blood test	✓	✓	✓	Х

Training and certification plans

(Prior to baseline assessment, Earlwood medical centre, approx. 50 min)

We will have the General Practitioners (GPs) who believed to meet GCP requirement with appropriate qualification and skill to conduct the trial and will have the 'study therapists' to assist them. 'Study therapists' must attend the compulsory training session for this research only prior to the commencement of the study, which will facilitate their understanding of the trial and their roles.

Information delivery session

(Baseline assessment only; Earlwood medical centre; approx. 30min)

- The importance of following study guidelines for adherence to daily study intervention;
- Instructions about taking supplements including dosage, storage and what to do in the event of a missed dose; notification there will be a pill count at every study visit;
- Instructions about how to apply the food list into real life and how to record daily dietary
 intake by using the smartphone application 'East Diet Diary' or by a paper-based food diary
 and what to do if miss to record; notification there will be a dietary diary examination at
 monthly study visit;

- Instructions about clothing, timing, weather condition for sun exposure and how to record daily sun exposure time on the paper-based diary and what to do if miss to record; notification there will be a sun exposure diary exam at monthly study visit;
- The importance of notifying the clinic if experiencing problems possibly related to study products such as side effects, upset symptoms, lost pills or food lists or diary books.

Anthropometry assessment

(Each visit; Earlwood Medical Centre; approx. 10min)

- Weight (kg) is measured by a digital scale (Tanita UM-051).
- BMI is calculated out based on equation: BMI=weight (kg)/height² (m²).
- Waist and hip ratio is measured by a measuring tape and calculated.

Data collection: dietary data exam / sun exposure exam/ pill count

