(Each visit, Earlwood medical centre, approx. 5min)

Adverse events will be collected after the participant has provided consent and enrolled

in the study. There is the possibility that in the dietary intervention group, some subjects may report food intolerance and/or allergy symptoms to seafood or dairy products. We will record the incidences; APD will provide dietetics consultation and appropriate suggestion to minimize the risks. If the adverse effects continue, participants will be excluded from the trial, allergy test and related medical treatment will be provided if necessary.

Blood test

(Baseline assessment, 3^{rd} month and 9^{th} month only; Earlwood medical centre; approx. 10 min)

 A government accredited Pathology Collection point or the Registered Nurses at Earlwood Medical Centre will collect the blood samples and forward the sample to the NATA accredited pathology laboratory to conduct the blood test for the Diabetes biomarker and serum 25OH D.

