5.4. RECRUITMENT AND SCREENING*

Trial information will be provided through website, flyer and local advertising. The trial will also be introduced to GPs and allied health professionals for cross-referral recruitment. Participants who express an interest through email, phone calls and personal attendance at clinics will be recruited. These include self-referred participants and participants who are referred by a GP or health professional. Diabetic patients' lists (name only) in both clinic centres will be used to contact for an EOI (expression of interest) as well. Responses to any inquiries about participation in the research study are to be answered by a phone that is manned during business hours and answered by voicemail at all other times. A research assistant will respond to each inquiry immediately, using a screening instrument to identify eligible participants and provide the following instructions.

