5.6. ENROLMENT PROCEDURE*

The research staff will enrol the participants following the confirmation of the consent form and eligibility.

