5.7. RANDOMISATION PROCEDURE

Allocation: Sequence generation

Participants will be randomly assigned to one of four different groups with an equal ratio referring to the permuted block randomisation. The software randomisation package MINUM will be used for sequence generation. The block sizes will not be disclosed, to ensure concealment.

Allocation concealment mechanism

Allocation concealment will be ensured, as the centre will not release the randomisation code until

the participants have been recruited into the trial. The randomisation will be conducted by an independent investigator (not the research student) and send the sequence to study therapists who are only responsible for implementing the randomisation.

Implementation

All participants who give consent for participation, and who fulfil the inclusion criteria, will be randomized. An independent investigator (not the research student) will send the randomisation instruction to the study therapist who is not involved in recruitment or outcome assessment. Follow the randomisation instrument, eligible study therapist prepares closed envelopes with printed randomisation numbers and are available in both recruitment centres. For every randomisation number, the corresponding code for the intervention group will be found inside the envelope. Only the study therapist will open the envelope and will find the treatment to be conducted for this participant. The therapist then gives the information about treatment that allocated to the patient. The randomisation list will be stored in the two centres for the whole time period of study.

6.SAFETY*

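### The protocol needs a 25OHD result before allocation but schedules no test to supply one, and its flow chart places the baseline assessment after randomisation

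*Protocol*

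**What the plan says.** **Entry criterion.** Protocol section 4.1, criterion 3, requires "Serum 25OHD is between 28 nmol/l and 85 nmol/l". This needs a laboratory value.

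**When eligibility is settled.** The section 5.2 table times the inclusion and exclusion check as "Prior to the initial visit". Section 5.6: "The research staff will enrol the participants following the confirmation of the consent form and eligibility". Section 5.7: "All participants who give consent for participation, and who fulfil the inclusion criteria, will be randomized".

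**How screening is done.** Section 5.4: "A research assistant will respond to each inquiry immediately, using a screening instrument to identify eligible participants". It mentions neither a blood sample nor a look-up of earlier results. Recruits include people who refer themselves as well as those sent by a GP or health professional.

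**When blood is taken.** The blood test entry in section 5.2 is headed "Baseline assessment, 3^{rd} month and 9^{th} month only; Earlwood medical centre; approx. 10 min". The section 5.2 table has no screening column.

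**Order of steps.** The section 5.1 flow chart lists screening and recruitment, consent, randomisation, the four arms with their interventions, and then the baseline assessment, which contains "Blood test (HbA1c, BSL, insulin and serum 25 OHD". The section 5.2 table, however, ticks the information session and informed consent at the baseline assessment. Section 5.5 goes from signing consent to attending baseline with no randomisation in between.

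**Who knows the arm.** In section 5.7 the therapist opens the envelope and tells the patient the allocation. Section 7 describes the therapist doing the baseline anthropometry, diet and sun assessments as blind, and the pathology technician likewise, but then says that neither participants nor assessors are blinded.

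**The concern.** The protocol makes allocation conditional on a laboratory result that none of its own procedures delivers in time. A site following the flow chart would first see a 25OHD value for someone already randomised. If the value is out of range, the site must either remove the participant, which is a post-randomisation exclusion, or keep someone who fails a stated entry criterion. The protocol does not say which.

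The same order affects the baseline data. The 24-hour food recall, the food frequency questionnaire and the sun exposure questionnaire are self-reports of the behaviours that two of the arms are asked to change. A participant who already knows the arm may answer differently. Attendance at the baseline visit may also depend on the arm, for instance among people told they are on the wait list, so some randomised participants could lack a baseline HbA1c. The section 8 analysis is a repeated-measures ANOVA with time as a factor and relies on a sound pre-treatment value.

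**Working it through.** **1. Can the 25OHD criterion be met by following the protocol?**

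| Step | Source | Relation to first study blood test |
|---|---|---|
| Eligibility check | 5.2 table | before the initial visit, so before it |
| Enrolment, once eligibility is confirmed | 5.6 | needs the 25OHD result |
| Randomisation of those meeting the criteria | 5.7 | needs the 25OHD result |
| First study blood test | 5.1, 5.2 | at baseline, listed after randomisation in 5.1 |

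Suppose the flow chart is set aside and the baseline draw is placed before randomisation. The 5.2 table still settles eligibility before the initial visit, so the sample still comes too late for that check. The gap therefore does not depend on the flow chart alone.

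**2. Is the order itself consistent?** Section 5.7 randomises people who have consented. The 5.2 table ticks consent at the baseline visit, so on that reading randomisation cannot come before the visit. The flow chart places it before. The two cannot both be followed.

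**3. How many could be out of range?** The protocol gives no 25OHD distribution, so the following are assumptions chosen to show a range. Normal: share outside = Φ((28 − mean)/SD) + 1 − Φ((85 − mean)/SD). Lognormal: the same on the log scale.

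| Assumed distribution (nmol/l) | Below 28 | Above 85 | Outside |
|---|---|---|---|
| Normal, mean 45, SD 20 | 0.198 | 0.023 | 22% |
| Normal, mean 55, SD 20 | 0.089 | 0.067 | 16% |
| Normal, mean 65, SD 22 | 0.046 | 0.182 | 23% |
| Lognormal, median 45, log-SD 0.45 | 0.146 | 0.079 | 22% |
| Lognormal, median 55, log-SD 0.45 | 0.067 | 0.167 | 23% |
| Lognormal, median 65, log-SD 0.45 | 0.031 | 0.276 | 31% |

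These shares apply only where no earlier result was used. Where a valid one always is, the share found late is 0. The working range is 0 to about 30%.

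**4. What would late exclusion cost?** The protocol's own sample size first: 7.849 × (0.35 × 0.65 + 0.70 × 0.30)/0.35² = 7.849 × 0.4375/0.1225 = 28.03, which agrees with the stated 28 per group.

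Using the same formula for power, with k = (N/4)(1 − q)(1 − d), where q is the share removed after randomisation and d is dropout, power = Φ(0.35/√(0.4375/k) − 1.96):

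| N randomised | d | q | k per arm | Power |
|---|---|---|---|---|
| 134 | 20% | 0 | 26.8 | 0.78 |
| 134 | 20% | 30% | 18.8 | 0.63 |
| 123 | 10% | 0 | 27.7 | 0.80 |
| 123 | 10% | 30% | 19.4 | 0.64 |

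This is an illustration in the protocol's own terms, a comparison of two proportions. It is not the power of the planned ANOVA on HbA1c.

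**The case against.** The strongest reply is that the protocol says three times that eligibility comes first (5.2 table, 5.6, 5.7). Recruitment runs through GP referral and both clinics' diabetic patient lists, so an existing pathology result is a plausible source. Other entry rules point the same way: section 4.2 excludes people on eGFR and for hypercalcaemia, and neither is in the listed study blood panel. The word restricting blood tests to three visits describes study visits and does not bar an earlier result. All of this stands. A reader might infer that the criterion cannot be checked before allocation at all; the text does not go that far. What remains is that no source or time window is named for a criterion that decides entry, and section 5.4 also admits self-referred people for whom no clinic result can be presumed.

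Second, the order rests on a flow chart read without its arrows, and the 5.2 table and section 5.5 fit a different sequence. That is fair. It makes the order inconsistent rather than settled, and the inconsistency itself needs repair.

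Third, a reader might infer that baseline HbA1c is biased by knowledge of the arm. The documents give little support for this: it is a laboratory assay, the technician is described as blind, and no section says an intervention starts before the blood draw. Nor does section 8 adjust for baseline covariates, so a claim that a contaminated covariate enters the model would have no basis. For staff, section 7 contradicts itself, so one cannot say firmly that the baseline assessor knows the arm. For participants, one can say so if the flow chart order is followed.

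**Conclusion.** The point holds as a defect of sequence and of an unsupplied entry value. The protocol requires a 25OHD result before allocation, schedules no test to provide it, names no alternative source or time window, and gives two incompatible orders for consent, randomisation and baseline. If the flow chart is followed, participants outside 28 to 85 nmol/l are found only after allocation. The baseline food recall, food frequency questionnaire, sun questionnaire and attendance are then open to influence from knowing the arm. Laboratory HbA1c is little affected.

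The size is unknown. It is 0 if a valid earlier result is always used, and up to about 30% of those randomised under the assumed distributions. A reader might multiply those shares by the planned 123 to 134 participants and quote a head count. The documents do not support a count, because they give no 25OHD distribution and do not exclude earlier results. The fall in power to roughly 0.63 or 0.64 is the far end of the illustration and assumes that everyone found out of range is removed. The defect in sequence does not depend on any of these figures.

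**What to change.** Align the section 5.1 flow chart, the section 5.2 table and blood test entry, section 5.7 and section 7 to one order:

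1. consent;
2. all baseline measurements and the baseline blood draw;
3. 25OHD criterion confirmed from that sample;
4. envelope opened;
5. arm-specific instructions given.

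Add to section 5.7 that no envelope is opened until the baseline data are recorded and the 25OHD criterion is confirmed. Move the eligibility row of the 5.2 table, and the place of consent, to match. In section 7, state once whether the person making the baseline assessment is blind; under this order, nobody knows the arm at baseline.

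A lighter alternative is to accept a recent earlier result, naming its source and time window. That closes the eligibility gap, but the baseline measurements would still need to be moved ahead of allocation.

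The cost is amendment wording and a wait for the laboratory between baseline and allocation. Section 5.2 gives the information session at the baseline visit only, so holding back its arm-specific part probably adds one further contact per participant. No extra blood sample is needed.
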